# 9. Schedule of Assessments

# 9.1. Eligibility Screen

The designated clinician will confirm discontinuation of standard 4-drug ATT due to a suspected DILI event. They will check the patient against the eligibility criteria, and they will approach the patient about the trial.

# 9.1.1.Informed Consent

Any patient identified as being potentially eligible for the trial will be given a PIS by a member of their usual care team and a member of the site research team will explain the trial the patient. Where a face-to-face visit is not possible e.g. due to social distancing measures, a copy of the PIS may be posted or provided electronically whichever is convenient to the patient and contact details provided so that the potential participant has the opportunity to discuss the study and ask questions before providing their consent to participate.

If a patient is interested in taking part, written informed consent will be obtained before any trial procedures are carried out, as described in section 5.2. If a face-to-face visit does not take place and consent is obtained remotely, site staff must have received the completed informed consent form (ICF) before issuing baseline questionnaires. This may be electronically or by post.

## 9.1.2. Baseline Assessments

Prior to randomisation, all relevant clinical data will be submitted to the DILI-adjudication panel. The panel will review the clinical information to determine that the patient is experiencing/has experienced a DILI event related to treatment of TB with standard 4-drug ATT. The patient will also be asked to complete the EQ-5D-5L, a quality-of-life questionnaire.

#### 9.1.3.Randomisation

Upon confirmation of DILI by the adjudication panel, randomisation will occur after the patient has recovered, and the attending clinician is prepared to re-commence treatment. The Principal Investigator or delegated site staff will randomise the patient using the online randomisation system via a secure website developed and maintained by NCTU.

#### 9.1.4.Prescribe/ issue trial treatment

# Phase A

[Begins within 2 days of randomisation]

- Reintroduction of treatment regimen (anticipated duration):
  - o 9 days for control arm
  - 7 days for intervention arm

#### Phase B

- EQ-5D-5L completion at W2 for both arms
  - Discontinuation of Drug(s) at W8:
    - Control Arm: E and Z
      - o Intervention Arm: E

Trial	TB-DILI Trial	Protocol	1.2	date:	02-Aug-2022	Page 33 of 58
name:		version:				

## DILI Recurrence

[Could occur at any timepoint during treatment period]

- EQ-5D-5L questionnaire
- Discontinuation of control or intervention ATT regimen

#### DILI Recovery

• EQ-5D-5L questionnaire

#### EoT

• EQ5D questionnaire is completed one week after the end of treatment: This is expected to be W25 for control arm and W37 for intervention arm

#### 12 Months Post Randomisation

[±28 days]

- EQ-5D-5L
- Collection of outcome data

## 9.2. Treatment discontinuation

Participants who discontinue the study treatment or change treatment for any reason will continue to be followed up in accordance with the trial schedule and continue to provide trial data, including completion of follow-up questionnaires for use in the analysis, unless they are unwilling to do so. All the data collected will be used, and any participant who discontinues study treatment will be reminded of the importance of continuing to complete study questionnaires/assessments.

Reasons for trial treatment discontinuation may include participant decision or significant adverse events.

#### 9.3. Withdrawal Procedures

Participants who do not adhere to allocated trial treatment are not required to withdraw.

#### 9.3.1. Withdrawal prior to randomisation

Any patients that request to withdraw their consent prior to randomisation will be withdrawn completely from the trial; they will not be randomised, and follow-up questionnaires will not be issued. They will be offered the opportunity to provide consent for their routine data to be used; see section 5.3.

#### 9.3.2. Discontinuation from trial follow-up/ other trial-related activities post randomisation

Participants may discontinue their contribution to follow-up and/or other trial-related activities, including receiving trial-related communications. The NCTU must be informed of all requests by participants to stop their involvement in the trial and appropriate action will be taken to ensure that the participants wishes are followed.

Sites will be trained to determine which activities the participant may wish to discontinue from

Trial	TB-DILI Trial	Protocol	1.2	date:	02-Aug-2022	Page 34 of 58
name:		version:				

Participants may discontinue one or all of the following activities:

Discontinuation type	Discontinuation procedure	Use of data that are already collected
Discontinue follow-up questionnaires	Any participant that requests to discontinue from trial follow-up procedures will still have their routine clinical data obtained.	N/A discontinue from follow- up procedures only
Discontinue from other trial communications	Any patient who requests to be withdrawn from other trial communications will be removed from all mailing lists for ongoing trial contact (e.g. newsletters and reminders) but will still receive trial questionnaires.	N/A withdrawal from communications only
Collection of data from medical records and/or NHS Digital	Any participant that requests to discontinue collection of routine data will be directed to the national data opt out service.	Any data collected prior to participant withdrawal will be retained and used.
Full trial withdrawal	Any participant that requests to have no further involvement in the trial will be marked as withdrawn on the trial database.	Any data collected prior to participant withdrawal will be retained and used unless the participant specifically requests that all their data is removed

If site staff are made aware of a participant's discontinuation from any trial activities, the PI or delegate should record this in the CRF as soon as possible to ensure the correct procedures are followed by NCTU and the site team. Participants will be asked their reason(s) for withdrawal but are not obliged to provide these.

Withdrawn participants will not be replaced. Data collected prior to withdrawal will be retained and used in the analysis as per described in the PIS. It should be made clear to any participant withdrawing consent for further data collection that data pertaining to safety will continue to be collected for regulatory purposes and will be included in any safety analysis and the final analysis. In addition, if any significant new information becomes available with regard to the treatment they received in the trial, it may be necessary to contact them in the future.

# 9.4. Losses to follow-up

If contact cannot be made and the participant has not withdrawn their consent to participation in the trial, outcome data will be obtained from medical records by the research team and/or NHS Digital where possible. If it is not possible to obtain the primary outcome, the participant will be designated as lost to follow-up for the primary outcome

Trial	TB-DILI Trial	Protocol	1.2	date:	02-Aug-2022	Page 35 of 58
name:		version:				

# 9.5. Protocol non-compliance

Protocol compliance will be assessed via central monitoring of eCRF data in accordance with the trial monitoring and data management plans. If a member of site staff is made aware of a non-compliance, they are advised to report this to the NCTU who can assess and record in the eCRF where appropriate.

# 10. Adverse Event Reporting

Adverse Event (AE)	Any untoward medical occurrence in a clinical trial participant administered a medicinal product and which does not necessarily have a causal relationship with this treatment.
	An AE can therefore be any unfavourable and unintended sign (including abnormal laboratory findings), symptom or disease temporally associated with the use of an investigational medicinal product, whether or not related to the investigational medicinal product.
Adverse Reaction (AR)	Any untoward and unintended responses to an IMP related to any dose administered.
	An AE judged by either the reporting Investigator or Sponsor as having causal relationship to the IMP qualifies as an AR. The expression reasonable causal relationship means to convey in general that there is evidence or argument to suggest a causal relationship.
Serious Adverse Event (SAE)	

Any untoward medical occurrence or effect that:

Results in death

Event (SAL)	
 
Is life-threatening*
 

	
 
Requires hospitalisation or prolongation of existing hospitalisation
 
Results in persistent or significant disability or incapacity
 
Is a congenital anomaly/birth defect
 

	
 
Or is otherwise considered medically significant by the Investigator**
 

	The term severe is often used to describe the intensity (severity) of a specific event. This is not the same as serious, which is based on participants/event outcome or action criteria.
	* Life threatening in the definition of an SAE refers to an event in which the participant was at risk of death at the time of the event; it does not refer to an event that hypothetically might have caused death if it were more severe.
	** Medical judgment should be exercised in deciding whether an AE is serious in other situations. Important AEs that are not immediately life threatening or do not result in death or hospitalisation but may jeopardise the participant or may require intervention to prevent one of the other outcomes listed in the definition above, should be considered serious.
Serious Adverse Reaction (SAR)	An Adverse Reaction which also meets the definition of a Serious Adverse Event

Trial	TB-DILI Trial	Protocol	1.2	date:	02-Aug-2022	Page 36 of 58
name:		version:				
Unexpected Adverse Reaction (UAR)	An AR, the nature or severity of which is not consistent with the applicable product information (e.g. Investigator Brochure for an unapproved IMP or Summary of Product Characteristics (SPC) for a licensed product). When the outcome of an AR is not consistent with the applicable product information the AR should be considered unexpected.					
--	---					
Suspected Unexpected Serious Adverse Reaction (SUSAR)	A SAR that is unexpected i.e. the nature, or severity of the event is not consistent with the applicable product information. A SUSAR should meet the definition of an AR, UAR and SAR.					

# 10.1. Adverse Events (AEs) and reporting requirement/ procedures

The collection and reporting of AEs will be in accordance with the Medicines for Human Use Clinical Trials Regulations 2004 (and subsequent amendments).

All IMPs being used in this trial are being used within license and have well characterised safety profiles.

The treatments provided to both randomised groups are widely available within the NHS, used in standard care and considered to be safe. Expected adverse events (listed in the table below) are as per the SmPC for trial treatments. These events are secondary outcomes and will be collected as part of the eCRF. Adverse events will be coded using the Medical Dictionary for Regulatory Activities (MedDRA) as per NCTU standard practice and the number of occurrences reviewed throughout the trial by the TMG and the Data Monitoring Committee (DMC).

Body system		Adverse event							
Blood and lymp	hatic system disorders	Agranulocytosis							
		Aplastic anaemia							
		Thromb	ocytopeni	а					
		Thromb	ocytopeni	a with	purpura				
		Neutro	penia						
		Eosinop	hilia						
		Leukop							
			lytic anaen						
		Dissemi	inated intr	avascu	lar coagu	ulation			
		Vitamin	K depend	ent coa	agulation	n disorders			
Congenital, fam	ilial, and genetic disorders	Porphy	ria						
Ear and labyrint	h disorders	Deafne	SS						
		Tinnitus	5						
		Vertigo							
Endocrine disor	ders	Adrenal insufficiency							
Eye disorders		Tear discolouration							
	Optic neuritis								
		Pyrexia							
Trial TB-DI name:	LI Trial		Protocol version:	1.2	date:	02-Aug-2022	Page 37 of 58		

# Table 4. Expected Adverse Events Associated with the Study Medication

conditions Hepatobiliary disorders Immune system disorders Infections and infestations Investigations	EdemaMalaiseFeverHepatitisHyperbilirubinemiaAnaphylactic reactionHypersensitivityPseudomembranous colitis					
Immune system disorders Infections and infestations	MalaiseFeverHepatitisHyperbilirubinemiaAnaphylactic reactionHypersensitivityPseudomembranous colitis					
Immune system disorders Infections and infestations	Fever   Hepatitis   Hyperbilirubinemia   Anaphylactic reaction   Hypersensitivity   Pseudomembranous colitis					
Immune system disorders Infections and infestations	HepatitisHyperbilirubinemiaAnaphylactic reactionHypersensitivityPseudomembranous colitis					
Immune system disorders Infections and infestations	HyperbilirubinemiaAnaphylactic reactionHypersensitivityPseudomembranous colitis					
Infections and infestations	Anaphylactic reaction Hypersensitivity Pseudomembranous colitis					
Infections and infestations	Hypersensitivity Pseudomembranous colitis					
	Pseudomembranous colitis					
Investigations	Influenza					
	Hepatic enzyme increased					
	Blood bilirubin increased					
	Aspartate aminotransferase increased					
	Alanine aminotransferase increased					
	Blood creatinine increased					
	Blood pressure decreased					
Metabolism and nutrition disorders	Acidosis					
	Hypoglycaemia					
	Nicotinic acid deficiency					
	Decreased appetite					
	Hyperuricaemia					
	Gout					
Musculoskeletal and connective tissue	Systemic lupus erythematosus					
disorders	Muscle weakness					
	Myopathy					
	Bone pain					
	Joint pains					
Nervous system disorders	Peripheral Neuropathy					
	Dizziness					
	Headache					
	Cerebral haemorrhage					
	Numbness					
	Paraesthesia of the extremities					
	Disorientation					
Pregnancy, puerperium and perinatal	Post-partum haemorrhage					
conditions	Fetal-maternal haemorrhage					
Psychiatric disorders	Elevated mood					
	Psychotic disorder					
	hallucinations					
	mental confusion					
Respiratory, thoracic and mediastinal	Interstitial lung disease					
disorders	Dyspnoea					
	Wheezing					
	Sputum discoloured					
	pulmonary infiltrates					
	Pneumonitis,					
Vascular Disorders	Vasculitis					
	Shock					
	Flushing					

Trial	TB-DILI Trial	Protocol	1.2	date:	02-Aug-2022	Page 38 of 58
name:		version:				

[	Vasculitis			
	Bleeding			
Gastrointestinal disorders	Constipation			
	Dry mouth Nausea			
	Pancreatitis acute			
	Nausea			
	Vomiting			
	Diarrhoea			
	Gastrointestinal disorder			
	Abdominal discomfort			
	Tooth discoloration			
	anorexia			
Hepatobiliary disorders	Hepatitis			
	Acute hepatic failure			
	Liver injury			
	Jaundice			
Skin and subcutaneous tissue disorders	Toxic epidermal necrolysis			
	eosinophilia systemic symptoms			
	Erythema multiforme			
	Stevens-Johnson syndrome			
	Rash			
	Pruritus			
	Urticaria			
	Dermatitis allergic			
	Pemphigoid			
	Sweat discoloration			
	Acute generalized exanthematous pustulosis (AGEP)			
Renal and urinary disorders	Dysuria			
	Acute kidney injury			
	Chromaturia			
	Interstitial nephritis			
Reproductive system and breast disorders	Gynaecomastia			
	Menstrual disorder			

# **10.2.** Serious Adverse Events and reporting requirements

Due to common use of these drugs in treating this disease, there is already an immense volume of safety data collected on these drugs. It is improbable that new SUSARs will be identified for the drugs in this trial. Data collection in TB-DILI will operate entirely from patient reported outcomes and there is no clinical routine follow-up once medication has been dispensed. As such, it is not likely that further details of any SAE will be available to the central study team, and any action/outcomes may only be known at the next data collation point. Although this limits the value of expedited reporting from either a safety or regulatory perspective, the processes in place still meet the Sponsor's legal obligations in terms of SUSAR reporting.

If an Investigator believes a particular SAE in a participant receiving the drugs is both unexpected and potentially due to the interventional drug (i.e. a SUSAR), they will be asked to complete a SAE report as soon as possible after becoming aware of the event.

ſ	Trial	TB-DILI Trial	Protocol	1.2	date:	02-Aug-2022	Page 39 of 58
	name:		version:				

Following review by the Chief Investigator/delegate, all confirmed SUSARs will be reported to the Chair of the DMC and to relevant regulatory authorities, Sponsor, ethics committees, and investigators in an expedited manner in accordance with regulatory requirements.

Safety information relating to adverse events not subject to expedited reporting that are captured as trial endpoints will be closely monitored by the DMC throughout the trial. The DMSC will be provided with a report (at a frequency [at least annual] specified by the DMSC) which will include the key safety-related trial outcomes.

# 10.3. Events that do not require reporting

Individuals who develop a DILI significant enough to require hospital admission are at high risk of developing other adverse events. To this end, anticipated events that are consequences of the underlying disease, common events in the study population, or are part of the primary and secondary outcomes will be exempt from expedited reporting. Adverse events that are not listed as expected events (table 4) and are not deemed as serious and related to trial treatment (i.e. a SUSAR) by the assessing clinician are also exempt from reporting.

A SAE judged by the Investigator or medical monitor (in this case the CI), to have a reasonable causal relationship with the trial medication will be regarded as a Serious Adverse Reaction (SAR). The medical monitor will also assess all SARs for expectedness. If the event meets the definition of a SAR that is unexpected (i.e. is not defined in the Reference Safety Information (RSI) –see Section 10.1) it will be classified as a SUSAR.

## **10.4.** SAE reporting Procedure – NCTU trial Office

Only SAEs that are deemed related by the assessing clinician (i.e. a SUSAR) need reporting. When completing the SAE form, the Investigator will be asked to define the causality and severity of the AE. The SAE form must be sent to the NCTU as soon as possible and no later than 24 hours after first becoming aware of the event (or obtaining the follow-up information from the participant).

On receipt, NCTU will allocate each SAE a unique reference number which will be forwarded to the site as proof of receipt within 1 working day. If confirmation is not received within 1 working day, the site should contact the NCTU. The SAE reference number will be quoted on all correspondence and follow-up reports regarding the SAE and filed with the actual SAE in the Site File and TMF.

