## Sites

For SAE Forms completed by someone other than the Investigator, the Investigator will be required to countersign the original SAE form to confirm agreement with the causality and severity assessments. The form should then be returned to NCTU and a copy kept in the Site File. Investigators should also report SAEs to their own Trust where required by local practice.

On becoming aware that a participant has experienced an SAE, the Investigator (or delegate) must complete, date and sign a SAE form. The form should be e-mailed to NCTU using the following e-mail address:

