# 10.6. Reporting period

Details of unexpected AEs (except those listed is section 10.1) will be documented and reported from the date of commencement of protocol defined treatment 12 months after randomisation. In the case where participants are still being treated at the 12-month follow-up, the reporting period will be extended to 3 months post the 12-month follow-up.

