# 10.8.2. Serious Adverse Reactions

The NCTU will report details of all SAEs and SARs (including SUSARs) to the MHRA and REC annually from the date of the Clinical Trial Authorisation, in the form of a Development Safety Update Report (DSUR).

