## 10.10. Data Monitoring Committee (DMC)

The independent DMC will review all SAEs.

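### Section 10 gives sites conflicting rules on which SAEs to report, mislabels related SAEs as SUSARs, and still promises the DMC, the MHRA and the REC all SAEs

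*Protocol*

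**What the plan says.** Three triggers for an SAE report appear within a few paragraphs of each other.

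- Section 10.2 asks for one when the investigator thinks an SAE is both unexpected and potentially due to the trial drug.
- The opening of section 10.4 sets the test at relatedness: "Only SAEs that are deemed related by the assessing clinician (i.e. a SUSAR) need reporting".
- The Sites text of section 10.4 sets no condition beyond seriousness: "On becoming aware that a participant has experienced an SAE, the Investigator (or delegate) must complete, date and sign a SAE form".

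Section 10.3 repeats the SUSAR gloss in its exemption. Adverse events that are not in Table 4 and that "are not deemed as serious and related to trial treatment (i.e. a SUSAR) by the assessing clinician are also exempt from reporting". Section 10.6 points the other way: "Details of unexpected AEs (except those listed is section 10.1) will be documented and reported".

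The downstream commitments carry no filter. Section 10.10: "The independent DMC will review all SAEs". Section 10.8.2: "The NCTU will report details of all SAEs and SARs (including SUSARs) to the MHRA and REC annually".

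Section 10.2 explains the limited reporting by saying that data come wholly from patient-reported outcomes and that "there is no clinical routine follow-up once medication has been dispensed".

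**The concern.** The stated aim in section 2.1 is to compare the relative safety and effectiveness of the two regimens. Table 3 shows that participants and site staff know the allocation. If a site clinician's opinion of relatedness decides whether an SAE is sent at all, that opinion is formed with knowledge of the arm, and the threshold may differ between a regimen that contains pyrazinamide and one that does not. The medical monitor's independent review of seriousness and causality in section 10.4 begins on receipt of a form, so it cannot correct a decision not to send one.

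There is also a practical cost. Section 12.2.1 names a low SAE reporting rate as a possible reason for a monitoring visit. That signal cannot be interpreted if sites follow different rules. SAEs that were never recorded may not be fully recoverable later.

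**Working it through.** No arithmetic applies. The check compares the definitions with the rules and then follows each kind of event through them.

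**Step 1: definitions.** The definitions table in section 10 makes a serious and related event a SAR. A SUSAR is a SAR whose nature or severity does not fit the product information. Section 10.3 has the medical monitor assess every SAR for expectedness, a step that comes after relatedness. Equating related SAEs with SUSARs, as 10.3 and 10.4 both do, skips that step. Taken literally, it leaves the monitor with no expected SARs to assess.

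**Step 2: following each event through the rules.**

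| Event | 10.2 trigger | 10.4 opening rule | 10.4 Sites text | Other capture |
|---|---|---|---|---|
| Related and unexpected SAE | Yes | Yes | Yes | – |
| Related SAE, expected (Table 4 type) | No | Yes on the word related; no on the gloss | Yes | eCRF as a listed event (10.1) |
| Unrelated SAE of a Table 4 type | No | No | Yes | eCRF as a listed event (10.1) |
| Unrelated death | No | No | Yes | Mortality at 12 months (2.2.2) |
| Unrelated, non-fatal SAE outside Table 4 | No | No | Yes | Exempt in 10.3; on its face covered by 10.6 |

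The three triggers agree only on the first row. The last row is the critical one. Its only routes are the Sites text, which conflicts with the opening of the same section, and 10.6, which conflicts with 10.3. Section 10.6 also names no form and no recipient. Section 15 records service use only where the TB team judges it relevant to TB care, so it is not a dependable substitute.

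**Step 3: the promises.** All SAEs in 10.8.2 and 10.10 means every row of the table. The opening rule of 10.4 delivers the first row, and the second if the gloss is ignored. The eCRF and mortality outcomes supply information on the second, third and fourth rows. However, the text does not say that seriousness is recorded by that route, so those events could not be tabulated as SAEs without more.

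**Step 4: the justification in 10.2.** It does not describe this trial. Section 4.2 asks sites to upload all LFTs performed. Section 9.4 takes outcome data from medical records. Section 11.1 lists medical notes as source data. Section 15 records clinic and home visits. The LFT schedule is suggested rather than mandated, so the evidence lies mainly in the use of records and visits.

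**The case against.** The strongest reply is that the damage is small and the documents already contain most of the cure.

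- **The review is still possible.** A reader might infer that review of all SAEs cannot be done. The Sites text, read alone, requires a form for every SAE, so the documents show contradictory instructions, not impossibility. This limits the point but does not answer it, because the Sites text can equally be read as procedure for events already caught by the opening rule.
- **Liver safety is covered elsewhere.** A reader might infer that serious liver events would be lost. They would not. DILI recurrence is the primary outcome, and its severity, graded up to death or transplantation in Table 2, is a secondary outcome judged by a blinded panel. Table 4 includes hepatitis, liver injury and acute hepatic failure, is collected on the eCRF and is reviewed by the TMG and DMC. This stands.
- **Listed events can still be SUSARs.** A reader might infer that a Table 4 event can never be one. By the protocol's definition, unusual severity can make a reaction unexpected, and section 10.5 makes the SmPC of the drugs being taken the reference.
- **Section 10.3 is narrower than it looks.** It exempts only events that are both unlisted and not serious-and-related, and the exemption for anticipated and outcome events is from expedited reporting only. This stands, but the last row of the table meets both conditions.
- **Selective reporting of SAEs is legitimate.** For licensed drugs in standard use, a protocol may limit which SAEs are expedited. That is so. The fault lies in promising review of all SAEs without a consistent rule for collecting them.

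**Conclusion.** The contradiction and the wrong SUSAR gloss are on the face of the protocol and need correcting. The consequence is conditional. If the opening rule of 10.4 and the exemption in 10.3 govern, SAEs that are non-fatal, outside Table 4 and judged unrelated by the site have no stated route to the trials unit, and the review promised to the DMC, MHRA and REC is incomplete for that class. If the Sites text governs, the defect is that sites have been given conflicting instructions. That the filter would act differently by arm is a possibility created by the open-label design; nothing in the protocol shows that it will.

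The size cannot be put as a count, because the protocol gives no rate for such events. A reader might combine the planning rates with the 5.3% acute liver failure figure in section 1.1: 175 × 0.10 + 175 × 0.015 = 20.1 recurrences, and 20.1 × 0.053 = 1.07, so about one liver failure missed. The documents do not support that use. The 5.3% describes those who develop DILI on anti-TB treatment, not recurrences after reintroduction, and such an event would be captured as an outcome in any case.

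The primary outcome, its adjudication and its analysis are untouched.

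**What to change.** 1. State one set of SAEs that sites must record. The preferred choice is every SAE, whatever its causality or expectedness, on the eCRF in both arms. Use the existing reporting period of section 10.6, including its three-month extension for participants still on treatment at 12 months; a plain cut-off at 12 months would drop that extension.
2. Tabulate these SAEs by arm for the DMC and supply them for the annual report. Define separately the subset that needs the 24-hour report.
3. Replace the SUSAR gloss in 10.3 and 10.4 so that seriousness, relatedness and expectedness are three judgements, with expectedness left to the medical monitor.
4. Bring 10.2, 10.3, both parts of 10.4, 10.6, 10.8.2 and 10.10 into agreement.
5. Correct the statement in 10.2 that there is only patient-reported data and no routine clinical follow-up, in line with sections 4.2, 9.4, 11.1 and 15.
6. If Table 4 and outcome events are to count towards the SAE review, record seriousness for them.

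Narrowing 10.8.2 and 10.10 to reported SAEs would also remove the contradiction, but it would give up the full review and keep the filter by unblinded opinion.

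The cost is protocol wording, one eCRF form and what should be a modest increase in site data entry; the protocol gives no figures from which to estimate that workload.
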